6.6.3.1. Investigator Assessment of Signs of Local Tolerance

The Investigator's assessment of local tolerance will consist of evaluation of signs of local skin reactions, which must be performed by a physician or trained evaluator during study site visits. At each study site visit, as indicated in Table 1, the application/administration site will be evaluated prior to study drug administration, 5 minutes after study drug administration (ie, immediately after patch removal for subjects receiving abaloparatide-sMTS), and 1 hour after study drug administration.

Investigators will assess each of the 12 signs of local skin reaction using a 4-point scale: 0-none, 1-mild, 2-moderate, and 3-severe. The 12 signs for local skin reactions are as follows: erythema, edema, vesiculation, glazed appearance, erosions, crusting, hyperpigmentation, hypopigmentation, scarring, atrophy, bruising, and bleeding.

If severe local skin reactions occur, Investigators should contact the Sponsor for further instructions. If sensitization is suspected, the Investigator should contact the Sponsor for further instructions and evaluation.

For any severe administration site reaction, the subject will be instructed to continue evaluations of the application site at 24-hour intervals until the skin irritation has stabilized or resolved. Any ongoing treatment-emergent local skin reactions noted at Month 12 will continue to be assessed at 24-hour intervals until resolved or stabilized.

Study sites will have access to a dermatology consultant for severe local skin reactions.

Events of ulcer, eschars, and non-healing wounds at the injection/application site will be evaluated as an AESI (ie, skin AESI).

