7.1.2. Serious Adverse Event

An SAE is any AE that results in any of the following:

- Death
- Life-threatening: The term "life-threatening" in the definition of "serious" refers to an event/reaction in which the subject was at risk of death at the time of the event/reaction; it does not refer to an event/reaction which hypothetically might have caused death if it were more severe
- Hospitalization or prolongation of existing hospitalization
- Persistent or significant disability/incapacity (ie, substantial disruption of the ability to conduct normal life function)
- Congenital anomaly/birth defect
- Important medical events that may not result in death, are life-threatening, or require hospitalization may be considered serious when, based upon appropriate medical judgment, they may jeopardize the subject and may require medical or surgical intervention to prevent 1 of the outcomes listed in this definition. Examples of such medical events include allergic bronchospasm requiring intensive treatment in an emergency room or at home, blood dyscrasias or convulsions that do not result in subject hospitalization, or the development of drug dependency or drug abuse

All AEs of osteosarcoma will be reported as SAEs.

All treatment-related AEs/SAEs must be followed until resolution (subject has returned to baseline status of health) or until stabilization (the Investigator does not expect any further improvement or worsening of the reported event), or until the subject is lost to follow-up.

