7.1.7. Follow-up of Adverse Events

All treatment-related AEs will be followed with appropriate medical management until resolved or stabilized. UADEs and MDRs will be followed until their medical outcome is determined, with periodic written reports about the status provided to the Sponsor.

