#### **4.6.2. Adverse Events of Special Interest**

An adverse event of special interest (AESI) is an AE that is designated to be of special medical or scientific interest to the Sponsor. There are four major categories of AESIs as follows:

- Administration site reaction AEs -- Skin reaction AEs at the injection/application site
- Skin AESIs -- AEs of eschar, ulcer, or non-healing wounds at the injection/application site
- Hypersensitivity AESIs -- TEAEs in the Hypersensitivity Standardized MedDRA Query (SMQ narrow)
- Other AESIs:
  - Orthostatic hypotension
  - Tachycardia
  - Nausea
  - Hypercalcemia
  - Hypercalciuria
  - Hypophosphataemia

The MedDRA PTs, High Level Terms (HLT), and SMQs used to identify the AESIs are stored in the study folder in the Biometrics SAS environment.

An overall summary of the treatment emergent AESIs will be provided, in which the number of subjects with any adverse events, number of subjects with any TEAEs, number of subjects with any treatment-related TEAEs, number of subjects with any severe TEAEs, number of subjects with any treatment-related severe TEAEs, number of subjects with any serious TEAEs, number of subjects with any treatment-related serious TEAEs, number of subjects with any TEAEs leading to study drug withdrawal, number of subjects with any TEAEs leading to study drug interruption, number of subjects with any TEAEs leading to study discontinuation, number of subjects with any TEAEs related to the device, and number of subjects with any TEAEs leading to death will be summarized by treatment group and overall.

The treatment emergent AESIs will be summarized by PT and SOC for each of the AESIs. Summary of the onset time and duration of the treatment emergent AESIs will be provided by

treatment group using descriptive statistics (number of subjects, mean, SD, median, interquartile range, minimum and maximum).

AESI onset time groups include:

- 1 day
- 2-3 days
- 4-7 days
- 8-15 days
- 16-29 days
- 1 to <2 months
- 2 to <6 months
- 6 to <10 months
- $\geq$ 10 months

AESI duration groups include:

- For Administration site reaction AEs, Skin AESI and Hypersensitivity AESIs:
  - < 1 hour
  - 1-<2 hours
  - 2-<4 hours
  - 4-<24 hours
  - 1-<2 day
  - 2-3 days
  - 4-7 days
  - 8-15 days
  - 16-29 days
  - >29 days
- For other AESIs:
  - 1-<2 day
  - 2-3 days
  - 4-7 days
  - 8-15 days
  - 16-29 days
  - >29 days

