For AESI duration, if there is more than one occurrence of the AESI for a subject, then the average duration for all occurrences for the subject will be used. If AE stop date is missing, then the last study date will be used. If both AE start date and AE stop date are missing, the AE duration will be missing.

To evaluate the relationship between AESIs and the antibody status, the incidence of treatment emergent AESIs will also be summarized by antibody status (ADA-, ADA+/Nab+, ADA+/Nab-, All ADA+, and Overall), SOC, and PT for both treatment groups.

An overall summary of the treatment emergent AESIs, as described above, will also be presented by treatment group (and overall) for the following subgroups:

- Age group (< 65, 65 - < 75, and  $\geq$  75 years)
- BMI group (BMI < 25,  $25 \leq$  BMI < 30, and BMI  $\geq$  30)
- Region (North America and Europe)

Subject listings will be provided for each of the AESIs.

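### A missing AESI stop date is replaced by the last study date, so ongoing events are summarised as complete and are not separated from resolved events of unknown date

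*SAP*

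**What the plan says.** SAP 4.6.2 plans onset-time and duration summaries for each AESI category. They are to be presented by "treatment group using descriptive statistics (number of subjects, mean, SD, median, interquartile range, minimum and maximum"), and also in duration bands whose top band is open-ended, above 29 days. Three rules govern the duration itself:

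- Missing stop date: "If AE stop date is missing, then the last study date will be used".
- Both dates missing: "If both AE start date and AE stop date are missing, the AE duration will be missing".
- Several occurrences in one subject: "then the average duration for all occurrences for the subject will be used".

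The SAP does not define the last study date. Section 4.6.2 mentions no censoring, no table of unresolved AESIs, and no distinction between an event that is ongoing and one that ended on an unrecorded date. Appendix A imputes AE start dates only.

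The skin category covers "AEs of eschar, ulcer, or non-healing wounds at the injection/application site". On follow-up, Protocol 6.6.3.1 says: "Any ongoing treatment-emergent local skin reactions noted at Month 12 will continue to be assessed at 24-hour intervals until resolved or stabilized". Protocol 7.1.7 says: "All treatment-related AEs will be followed with appropriate medical management until resolved or stabilized". Protocol 7.1.2 lets follow-up of treatment-related events run to resolution "or until stabilization (the Investigator does not expect any further improvement or worsening of the reported event").

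**The concern.** A duration that is still running when observation ends is right-censored: the true value is at least the observed one. Entering the observed value as a finished duration and taking an ordinary mean or median treats a lower bound as a measurement. The categories most exposed are those in which persistence matters, such as non-healing wounds.

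A second, opposite problem sits inside the same rule. It applies to every missing stop date, so a brief reaction that ended without its date being recorded is stretched to the end of the study.

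At stake is how the patch's local tolerability is described. Safety and tolerability are part of the study objective (Protocol 2.1; SAP 1.1), and a reader of the planned duration table could not tell how many durations are measured, how many are lower bounds, and how many are artefacts of a missing date.

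**Working it through.** **Inputs.** A month is 30 days (Protocol 3.1). Month 12 is Day 360 (SAP Table 2). The follow-up visit is 1 month ± 4 days after Month 12/EOT (Protocol Table 1, note 21), that is, Day 386 to 394 if EOT falls on Day 360. The documents give no expected number of open AESIs and no expected durations, so there is no planned figure to reproduce. I assume that a completer's last study date is the follow-up visit and that days are counted inclusively.

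**Step 1: value given to an open event in a completer.** Assigned duration = last study date − onset day + 1.

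| Onset | Follow-up on Day 386 | Day 390 | Day 394 |
|---|---|---|---|
| Day 90 | 297 | 301 | 305 |
| Day 300 | 87 | 91 | 95 |
| Day 330 | 57 | 61 | 65 |
| Day 360 | 27 | 31 | 35 |

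The value depends only on onset, not on how long the reaction really lasts. The event falls in the top band when onset is no later than the follow-up day minus 29: Day 357, 361 or 365. Nearly every single open event in a completer is therefore banded correctly.

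**Step 2: effect on the mean when events are truly ongoing.** Assumptions, none of them in the documents: exponential durations with mean m, onset uniform over Days 1 to 360, last study date Day 390, and no stop date ever obtained after it. Available follow-up is then uniform from 30 to 389 days, and the mean under the rule is

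m × {1 − (m/359) × [exp(−30/m) − exp(−389/m)]}.

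For m = 90: (90/359) × (0.7165 − 0.0133) = 0.176, and 90 × 0.824 = 74.1 days. A simulation of 400,000 events per setting agrees, and adds cases in which 15% or 30% of events have an earlier last study date, uniform between onset and Day 390:

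| True mean (days) | No early exits | 15% early | 30% early | Error in mean |
|---|---|---|---|---|
| 7 | 7.0 | 6.9 | 6.9 | 0% to −2% |
| 30 | 29.1 | 28.3 | 27.6 | −3% to −8% |
| 90 | 74.1 | 70.6 | 66.9 | −18% to −25% |
| 180 | 114.1 | 107.0 | 100.6 | −37% to −44% |

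At a true mean of 90 days the median falls from about 62 to between 49 and 56 days. The share above 29 days is 72% in truth, 72% with no early exits, and 68% with 30% early exits. Dividing total event-days by the number of resolved events, which treats open events as censored, returns the true mean to within 0.5 day in every setting. That is expected here, because the simulated durations are exponential and the censoring is non-informative.

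**Step 3: effect when the event resolved but the date is missing.** Take reactions that all last 1 day, with a fraction p lacking a stop date. Mean onset is Day 180.5, so the mean assigned value is 390 − 180.5 + 1 = 210.5 days. The mean under the rule is (1 − p) × 1 + p × 210.5: about 3.1 days for p = 1%, 5.2 for 2% and 11.5 for 5% (simulated: 3.1, 5.1, 11.4). A small fraction of missing dates is enough to move the mean upward.

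**Step 4: averaging within a subject.** One open 61-day event (Step 1, onset Day 330) with two 1-day events averages (61 + 1 + 1)/3 = 21 days and leaves the top band. With ten 1-day events it averages 71/11 = 6.5 days. Protocol 7.1.4 also has an event re-recorded with new onset and stop dates when its intensity changes over more than a day, so one long reaction can enter the average as several shorter ones.

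**The case against.** The tempting stronger reading is that the longest-lasting skin reactions are given artificially short durations, that the bias is downward, and that it is larger in the patch arm. The documents do not support that.

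- The rule covers all missing stop dates, and Step 3 shows that it can lengthen durations substantially. The planned bands start below 1 hour, so very brief reactions are expected. The direction is not fixed, and no document figure says which arm has more open events.
- In completers the assigned values are long and generally land in the open-ended top band. Misbanding a single event needs an onset close to the last study date, mostly through early exit.
- The protocol reduces the number of open events. Related events and skin reactions ongoing at Month 12 are followed to resolution or stabilization, and Protocol 7.1.3.1 asks for serial photographs of skin AESIs until they have fully resolved. A reaction open at the follow-up visit may still acquire a real stop date. Nor does Protocol 7.1.2 say that a stabilized event is left without one.
- Duration is not itself a named endpoint, the safety analyses are descriptive (SAP 4.6), and persistence can be seen in the by-visit local tolerance tables and the AESI listings.

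All of this limits the size of the problem, and none of it removes the core. The mean, SD and maximum still treat lower bounds as complete values. The top band does not protect a subject whose long event is averaged with short ones. Investigator local tolerance scores stop at Month 12 in the schedule, and listings are not a count. No planned table shows how many AESIs in each arm were unresolved.

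**Conclusion.** The point holds in a limited form. SAP 4.6.2 treats AESIs that are open at the last study date as finished. For those events the mean and maximum are understated, and so is the median if they are common. For resolved events with an unrecorded date, duration is overstated. The net direction and the arm more affected cannot be determined from the documents.

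The size depends on quantities the plan does not give. For ongoing events the shortfall in the mean runs from 0% to 2% at a true mean of 7 days up to 37% to 44% at 180 days, under the exponential, uniform-onset and early-exit assumptions in Step 2. The larger figures require reactions that typically last months.

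The band above 29 days is largely unaffected in completers, apart from dilution by per-subject averaging. The primary non-inferiority analysis and the sample size do not use these durations. This is a minor, cheap improvement to a descriptive safety table.

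**What to change.** In SAP 4.6.2:

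1. Define the last study date, including how it is set for a subject who leaves early and for a reaction followed beyond the follow-up visit.
2. Separate events that are ongoing from events that resolved on an unknown date. Count the second group and do not stretch those events to the end of the study.
3. Tabulate, by arm and AESI category, the number and percentage of AESIs unresolved at the last study date.
4. Report Kaplan-Meier median duration with ongoing events censored at that date.
5. State the unit of analysis when a subject has several occurrences, for example the longest episode per subject, and how records split by intensity are joined.

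The cost is a little more analysis. The SAP already uses Kaplan-Meier methods for study withdrawal (4.1) and clinical fracture (4.4.5.2). The change should need no new data, assuming the AE form records an ongoing status or outcome. Appendix A uses such a flag for medications, but the documents do not describe one for AEs. If the change comes too late for the SAP, SAP Section 1 provides for identifying it in Section 9.8 of the clinical study report.

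One downside remains. Kaplan-Meier assumes non-informative censoring, and excessive skin reactions are themselves a listed reason for stopping (Protocol 4.3.1). The count in item 3 should therefore stand beside the median.

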#### **4.6.3. Anti-Drug Antibody**

The ADA assessment in the serum samples for immunogenicity testing will be categorized by 2 outcomes:

- Negative for anti-drug antibodies
- Positive for anti-drug antibodies

The number (%) of subjects in the above categories of abaloparatide antibodies will be summarized at Day 1 (Visit 3), Day 14 (Visit 4), Month 1 (Visit 5), Month 3 (Visit 7), Month 6 (Visit 10), Month 9 (Visit 13), Month 12/EOT (Visit 16), and 30 days following the last dose of study drug (Month 13/Visit 17/EOS) by treatment group using the Antibody population.

For those subjects with anti-abaloparatide antibody present (i.e., are ADA positive), the titer level, the presence of neutralizing anti-abaloparatide antibodies (negative or positive), and the assessment outcomes for cross-reactivity to parathyroid hormone (PTH) (negative or positive) and parathyroid hormone-related peptide (PThrP) antibodies (negative or positive) together with the neutralizing antibody status in subjects that are positive for PTH (negative or positive for the presence of PTH-neutralizing antibodies) or PThrP (negative or positive for the presence of PThrP-neutralizing antibodies) will be summarized by study visit. Figures for the incidence of antibody and neutralizing antibody for the anti-abaloparatide, anti-PTH, and anti-PThrP will be presented by nominal visit.

All antibody information will be presented in a data listing.

The results of antibody analyses will be presented in a separate report.

#### **4.6.4. Local Tolerance**

Local tolerance will be assessed by the investigator and by the subject separately using a 4-point scale (0 = None, 1 = Mild, 2 = Moderate, 3 = Severe).

#### **4.6.4.1. Investigator Assessment of Local Tolerance**

Investigators will assess each of the 12 signs of local skin reaction. The 12 signs for local skin reactions are as follows:

- erythema
- edema
- vesiculation
- glazed appearance
- erosions
- crusting
- hyperpigmentation
- hypopigmentation
- scarring
- atrophy
- bruising
- bleeding

Investigators will evaluate the injection/application site at each study site visit prior to study drug administration, 5 minutes after study drug administration (i.e., immediately after patch removal for subjects receiving abaloparatide-sMTS), and 1 hour after study drug administration.

For each local skin reaction symptom, descriptive statistics (number of subjects, mean, SD, median, interquartile range, minimum and maximum) will be used to summarize the responses on the 4-point scale (0=None, 1=Mild, 2=Moderate, 3=Severe) by treatment, visit and timepoint. In addition, for each symptom, the number (%) of subjects in each response category (none, mild, moderate, and severe) will be provided by treatment per visit and timepoint.

The maximum severity of each symptom of local skin reaction per subject will be summarized with the number (%) of subjects in each response category (none, mild, moderate, and severe) by treatment and visit. The maximum severity of each symptom of local skin reaction per subject will also be summarized with the number (%) of subjects in each response category by treatment and timepoint (and at post-dose timepoint).

The maximum severity of symptom scores will also be summarized descriptively (number of subjects, mean, SD, median, interquartile range, minimum and maximum) for each response on the 4-point scale (0=None, 1=Mild, 2=Moderate, 3=Severe) by treatment and visit, and by treatment and timepoint, respectively.

All summary tables described above will be repeated by patch type (ultra-low bioburden, sterile) for all subjects in the abaloparatide-sMTS group.

During the COVID-19 pandemic, the investigator's assessment of the symptoms of local skin reactions may be assessed through alternative methods other than direct on-site assessment. To explore the impact of the COVID-19 pandemic, summaries of the investigator's assessment of local tolerance will also be presented by:

- region (North America and Europe)
- excluding local tolerance assessments made via alternative methods other than direct on-site assessment

All local tolerance scores assessed by the investigator will be presented in a listing.

#### **4.6.4.2. Subject Assessment of Local Tolerance**

Subjects will be instructed to perform a daily self-assessment of symptoms of local skin reactions at the administration site beginning on Day 1 through the Month 12/EOT visit. The assessments include:

- pain
- itching
- burning
- tenderness
- swelling

Subjects will evaluate the injection/application site prior to study drug administration, 5 minutes after study drug administration (i.e., immediately after patch removal for subjects receiving abaloparatide-sMTS), and 1 hour after study drug administration.

For each subject, the following local tolerance scores will be derived for each skin reaction symptom:

- the mean of the local tolerance scores across the entire treatment period by time point
- the maximum severity of local tolerance scores across the entire treatment period by time point

For each local skin reaction symptom, descriptive statistics (number of subjects, mean, SD, median, interquartile range, minimum and maximum) will be used to summarize both derived scores above:

- by treatment, visit and timepoint
- by treatment and visit
- by treatment and timepoint

In addition, for each symptom, the number (%) of subjects in each response category (none, mild, moderate, and severe) will be provided for the maximum severity of local tolerance scores:

- by treatment, visit and timepoint
- by treatment and visit
- by treatment and timepoint

For subjects in the abaloparatide-sMTS group, descriptive analysis described above for both mean and maximum severity of local tolerance scores will be performed by timepoint and patch type (ultra-low bioburden, sterile).

In addition, the mean of the (subject) local tolerance scores will be calculated for each month (visit period). Data for the Month 1 visit period will consist of subject assessments from Day 1 to the day of the Month 1 visit; data for the Month 2 visit period will consist of assessments from the day after the Month 1 visit to the day of the Month 2 visit; data for the Month 3 visit period will consist of assessments from the day after the Month 2 visit to the day of the Month 3 visit; and similarly for the visit periods for Months 4, 5, 6, 7, 8, 9, 10, 11, and 12. If the subject missed a visit, the ideal visit date will be used as a cutoff date for calculating the subject's local tolerance scores for the corresponding visit periods.

All the analysis for subject's local tolerance scores will be repeated with only the days of site visits included.

All local tolerance scores by the subject will be presented in a listing.

All summary tables described above will be repeated by patch type (ultra-low bioburden, sterile) for all subjects in the abaloparatide-sMTS group.

#### **4.6.5.      Laboratory Data**

Clinical laboratory values will be provided in conventional units and in standard international (SI) units by the central laboratory, unless otherwise specified.

In this study, local labs were allowed for screening. In addition, the original central lab was [REDACTED] Midway through the study, [REDACTED] was replaced with Medpace. Normal values of laboratory parameters in this study were provided by different local and central laboratories with inconsistent units and normal ranges. Thus, all numerical values will be converted to SI units and normalized to a standard set of reference/normal ranges as described by Chuang-Stein (1992 and 2001). The normalization process will be performed separately for each of the laboratory parameters as described in [Appendix D](#), using the Medpace normal ranges as the reference ranges.

Summaries of laboratory data will be presented using normalized laboratory values. Summaries using descriptive statistics by treatment group and study visit will be presented based on the SI units, including absolute results and changes from baseline. This includes serum chemistry, hematology, coagulation, urinalysis (for quantitative urinalysis assays), hormones and Vitamin D. In the event of repeat assessments, the last non-missing value per study day/time will be used in the summary statistics. Results from unscheduled visits will not be included in the descriptive summary tables.

Tables for the shift of laboratory data from baseline to the worst post-baseline value and from baseline to Month 12 (Visit 16) will be presented by treatment group. Results for serum chemistry, hematology, coagulation, and urinalysis will be presented by category (above normal limit, within normal limit, below normal limit). For shift tables from baseline to worst post-baseline value, and for baseline to Month 12, percentages will only be calculated based on the number of subjects with valid data for baseline and post-baseline; subjects who are missing either assessment will not be included in the percentage calculation (numerator or denominator). Results from repeat/unscheduled visits will be included in the shift analyses, as applicable.

Summaries of all laboratory parameters will also be presented by region (North America and Europe).

Any laboratory parameter value that is provided as “*< numeric value*” or “*> numeric value*” will be imputed as the *numeric value* in all summary tables and analyses, but will be shown with the actual result in the listings.

All laboratory data, including repeat and unscheduled assessments, will be presented in data listings, with indication of higher or lower than the associated normal range of each laboratory test, where applicable. Lab listings will show values in original results (in conventional units), results in SI units, and normalized values.

